Patients presenting to the emergency department, or needing hospitalization, for a variety of medical conditions often require Non-Invasive Ventilation (NIV). These patients` condition often requires close and continuous support by a staff member, putting these staff members at increased exposure to respiratory aerosols which could possibly contain SARS-CoV-2 of other airborne pathogens.

The “Lumena” mask is a disposable, single-patient, adult Oro-nasal mask, intended to provide a patient interface for transmission of NIV while minimizing dispersion of bio-aerosols from and into the breathing surrounding. It makes use of a dual layered containment space being constantly depressurized into a filtration system, thus allowing safety of use with non-hermetically sealed devices.

The mask has been approved by the Israeli Ministry of Health ("AMAR" / אמ"ר) as a medical device based on its intrinsic properties. This mask has undergone pre-clinical testing and is approved for marketing in several authorities. Inspir Labs, the sponsor is ISO 13485 certified. The purpose of this study is to evaluate the safety, usability and effectiveness of the Lumena mask and its ability to prevent the spread of respiratory aerosols in a real-world clinical setting.

3. Study Objectives:

3.1. Primary objective:

To assess the safety of the Lumena mask, compared to commercially available, commonly used oro-nasal face masks.

3.2. Secondary objectives:

- 3.2.1. To assess the effectiveness of the Lumena mask in achieving pre-defined clinical endpoints (i.e. oxygenation and ventilation), compared to commercially available, commonly used oro-nasal face masks.

	Date 1 st Issued: 26.12.2021	
Title: Clinical trials protocol – “Lumena”; Safety and usability of the LUMENA non-invasive ventilation mask	Doc #: CL-003	Revision: 04
	Confidential	Page 7 of 20

- 3.2.2. To assess the effectiveness of the Lumena mask in reducing the spread of respiratory aerosol in the patient's environment, compared to commercially available, commonly used Oro-nasal face masks.
- 3.2.3. To assess patient comfort and satisfaction while using the Lumena mask, compared to commercially available, commonly used Oro-nasal face masks.
- 3.2.4. To assess staff ease of use and overall satisfaction with using the Lumena mask, compared to commercially available, commonly used Oro-nasal masks.

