- 3.2.5. To assess the effectiveness of the Lumena mask in prevention of spread of respiratory particles during positive-pressure non-invasive ventilation within the Intensive Care Unit.

4. Sex:

Study will include both females and males, with at least 20% of patients being females.

5. Ages:

18 years and over

Title:

Clinical trials protocol – “Lumena”;

Safety and usability of the LUMENA non-invasive ventilation mask

Doc #: CL-003

Revision: 04

Confidential

Page 8 of 20

6. Number of patients:

6.1. 40 patients will be included in the study, until reaching 5 patients for each group.

Patients who drop out of the study for any reason will be replaced.

6.2. The study will be designed to contain 4 groups, each containing 5 patients.

6.3. The trial is designed as a crossover trial, as all patients will be required to use both Lumena mask and the control mask. The order of interventions is determined by the designated group. Prior to every inhalation and particle sampling, a baseline sample will be taken to filter possible carryovers from previous sampling.

Table 1 - Crossover Groups & Periods

Group	Period 1	Period 2	Period 3
A	Standard	Lumena No Suction	Lumena Suction
B	Standard	Lumena Suction	Lumena No Suction
C	Lumena No Suction	Lumena Suction	Standard
D	Lumena Suction	Lumena No Suction	Standard

	Date 1 st Issued: 26.12.2021	
Title: Clinical trials protocol – “Lumena”; Safety and usability of the LUMENA non-invasive ventilation mask	Doc #: CL-003	Revision: 04
	Confidential	Page 9 of 20

7. Statistical analysis:

Statistical analysis will be conducted following conclusion of the trial. A pre-test for the assumption of negligible carryover will be conducted as specified below:

$$T = \sqrt{\frac{mn}{N}} \frac{\bar{C}(X) - \bar{C}(Y)}{\sqrt{(SQ_{CX} + SQ_{CY}) / (N - 2)}}$$

After which a test for differences between treatment effects will be carried, according to the same formula but applying it to within-subject differences⁹

8. Inclusion Criteria:

- 8.1. Adults males and females aged 18 years and over.
- 8.2. Suffering from hypoxemic and/or hypercarbic respiratory failure requiring non-invasive ventilation and selected by medical staff to use CPAP or BiPAP.
- 8.3. Fully conscious (Glasgow Coma Scale 14-15) and able to cooperate with non-invasive ventilation.
- 8.4. Able to provide informed consent to participate in the study.

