- 15.10. Estimation of patient comfort – the question will be directed to the staff member. (an analog 1-5 scale as well as recording of verbal comments). – the question shall be phrased thusly: In a scale of 1-5, 1 being very uncomfortable and 5 being very comfortable ,how would you rate the patient's feeling with the experimental mask?
- 15.11. Device related adverse events will be reported by number, type, seriousness, severity , duration and attribution . All device and treatment related adverse events will be captured, regardless of severity.

16. Risk-Benefit Assessment

This is a feasibility proof of concept study, i.e. the nature and purpose of this study is to collect data to support research and development of the Lumena mask during noninvasive ventilation. The patients will have no direct health benefit from the use of the device.

	Date 1 st Issued: 26.12.2021	
Title: Clinical trials protocol – “Lumena”; Safety and usability of the LUMENA non-invasive ventilation mask	Doc #: CL-003	Revision: 04
	Confidential	Page 18 of 20

Expected benefit for patients and staff will arise from the future creation a safer care environment, potentially minimizing the need for bulky personal protective equipment (PPE).

The Lumena mask is considered class II device in Europe. Risk assessment has been performed and no major or intolerable risks were found. All the mitigations were documented. The risk management summary in the company’s IB demonstrates that the risks associated with the tested devices are well mitigated and are as low as reasonably practicable as defined by the applicable standards.

As for the Lumena mask usage, the protocol has been designed to decrease and minimize the risk to the patients by monitoring the respiratory parameters and using it for no more than an hour.

Expected adverse events like cough or bronchospasm may arise during inhalation study. Subjects will be monitored closely for safety and reporting of adverse events during the study including follow up until complete resolution of any adverse events.

17. Confidentiality and Information Security

Each patient will be assigned a unique identifying number and that number will be used throughout all data collection and analysis processes.

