The mapping of study identifiers and patient details will be stored by the primary investigator in a locked cabinet or a password-protected hospital-issued computer. The mapping list will be deleted or physically destroyed after completion of data analysis, and a report of said deletion will be included in the study summary. This file will not be sent via unencrypted email nor will it be removed from hospital premises without written consent by the hospital’s R&D division.

	Date 1 st Issued: 26.12.2021	
Title: Clinical trials protocol – “Lumena”; Safety and usability of the LUMENA non-invasive ventilation mask	Doc #: CL-003	Revision: 04
	Confidential	Page 19 of 20

Only the primary and secondary investigators, who are hospital employees with permission to access medical records, will have access to the de-identified data. Specifically, the sponsor will not have access to de-identified patient data.

18. Study Duration:

18 months or until enrollment of 40 eligible patients (the first of both occurrences).

Each patient will be included for a maximum of one day, from enrollment and obtainment of informed consent until end of participation.

	Date 1 st Issued: 26.12.2021	
Title: Clinical trials protocol – “Lumena”; Safety and usability of the LUMENA non-invasive ventilation mask	Doc #: CL-003	Revision: 04
	Confidential	Page 20 of 20

19. References:

1. Hannah Ritchie, Edouard Mathieu, Lucas Rodés-Guirao, Cameron Appel, Charlie Giattino, Esteban Ortiz-Ospina, Joe Hasell, Bobbie Macdonald, Diana Beltekian and Max Roser (2020) - "Coronavirus Pandemic (COVID-19)". Published online at OurWorldInData.org. Retrieved from: 'https://ourworldindata.org/coronavirus' [Online Resource]
2. Sergio Alejandro Gómez-Ochoa, Oscar H Franco, Lyda Z Rojas, Peter Francis Raguindin, Zayne Milena Roa-Díaz, Beatrice Minder Wyssmann, Sandra Lucrecia Romero Guevara, Luis Eduardo Echeverría, Marija Glisic, Taulant Muka, COVID-19 in Health-Care Workers: A Living Systematic Review and Meta-Analysis of Prevalence, Risk Factors, Clinical Characteristics, and Outcomes, *American Journal of Epidemiology*, Volume 190, Issue 1, January 2021, Pages 161–175, <https://doi.org/10.1093/aje/kwaa191>

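### The only comparative inference the protocol states is a test for differences, which could not support a conclusion that Lumena is as safe as the standard mask

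*Protocol*

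**What the plan says.** The primary objective in 3.1 is comparative: "To assess the safety of the Lumena mask, compared to commercially available, commonly used oro-nasal face masks". Objective 3.2.1 compares oxygenation and ventilation with the same standard masks.

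Section 7 describes a pre-test for carryover and then states that "a test for differences between treatment effects will be carried", using the pre-test formula on each patient's differences. It names no endpoint or objective, and gives no alpha, margin, confidence interval or upper bound. Section 15.11 adds that device-related adverse events are reported by count, type, seriousness and similar attributes, without a comparison between masks.

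Section 16 describes the trial as a feasibility study and says: "The patients will have no direct health benefit from the use of the device".

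The number of patients is given in two ways. Section 6.2 says "The study will be designed to contain 4 groups, each containing 5 patients", which makes 20. Section 6.1 says "40 patients will be included in the study, until reaching 5 patients for each group", and section 18 stops enrolment at "18 months or until enrollment of 40 eligible patients (the first of both occurrences". Both numbers are carried through below.

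**The concern.** For 3.1 and 3.2.1 the patient is not expected to gain from the new mask, so a favourable answer would be that it is not materially worse than the standard one. A test of the null of no difference cannot give that answer. If it rejects, it may show harm or benefit. If it does not reject, it shows little, and the fewer the patients, the more often it will not reject.

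If section 7 is applied to these outcomes as it stands, a moderately worse mask will often give a non-significant result that can be taken for comparable safety. That reading would reflect the sample size as much as the mask. The same data give an interval that says directly how much harm has been excluded. The mismatch between test and question would remain if the crossover model were fully specified and the sample size settled.

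**Working it through.** The protocol states no power, alpha, effect size or SD, so it has no figure of its own to reproduce.

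**Inputs**
- From the protocol: the section 7 statistic, with N − 2 in its variance term; N = 20 (6.2) or N = 40 (6.1, section 18); every patient uses both masks (6.3).
- Assumed: two-sided alpha 0.05; groups A and B (standard first) set against C and D (standard last), so m = n = N/2; effect d in SDs of the within-subject difference.

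**Continuous outcomes.** With m = n = N/2, √(mn/N) = √N/2. A treatment effect δ moves the within-subject period difference by +δ in one set of groups and −δ in the other, so the group means differ by 2δ. The noncentrality is (√N/2) × 2δ/SD = d√N, with N − 2 degrees of freedom.

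| N | d | Noncentrality | Critical t | Missed |
|---|---|---|---|---|
| 20 | 0.5 | 0.5 × 4.472 = 2.236 | 2.101 (18 df) | 43.8% |
| 20 | 0.3 | 0.3 × 4.472 = 1.342 | 2.101 | 75% |
| 40 | 0.5 | 0.5 × 6.325 = 3.162 | 2.024 (38 df) | 13.1% |
| 40 | 0.3 | 0.3 × 6.325 = 1.897 | 2.024 | 54% |

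A simulation of the section 7 formula (100,000 trials, N = 20, d = 0.5) gave 43.9%. Power of 80% is reached at d of about 0.66 with 20 patients and 0.455 with 40.

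**Sensitivity to the assumptions.** At N = 20 and d = 0.5, a one-sided 0.05 test misses 30.6%. If 0.5 SD is meant in units of the outcome SD, then d = 0.5/√(2(1 − ρ)), where ρ is the within-patient correlation:

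| ρ | 0 | 0.3 | 0.5 | 0.7 | 0.8 |
|---|---|---|---|---|---|
| Missed, N = 20 | 68% | 57% | 44% | 22% | 8% |
| Missed, N = 40 | 41% | 26% | 13% | 2% | 0.2% |

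**Adverse events.** An SD shift is not a natural scale here. Suppose an event that occurs only on Lumena. In simulation, the section 7 statistic misses a 10% excess risk 87% of the time at N = 20 and 42% at N = 40. At N = 20 the statistic is undefined in about 12% of trials (chiefly those with no events, 0.9^20 = 0.12), counted as not significant. A 20% excess at N = 20 is missed about 41% of the time.

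**What an interval would say.**
- The 95% half-width is critical t/√N: 2.101/4.472 = 0.47 SD at N = 20 and 2.024/6.325 = 0.32 SD at N = 40.
- With no events, the one-sided 95% upper bound is 1 − 0.05^(1/N): 13.9% at N = 20 and 7.2% at N = 40. The upper limit of a two-sided 95% interval, 1 − 0.025^(1/N), is 16.8% and 8.8%.

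**The case against.** The strongest reply is that the protocol does not commit the error. Section 7 does not assign its test to safety. The carryover remark in 6.3 concerns particle sampling, so section 7 may have been written with aerosol in mind, where a difference test is right. Section 15.11 already gives a descriptive route for adverse events. The objective is to assess safety, in a feasibility study, and no equivalence claim is written. Intervals and rules of interpretation are often left to a statistical analysis plan, and one may exist.

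Much of this stands. A reader might infer that the protocol will declare Lumena safe when the test is non-significant, or that it expressly names this test as the safety analysis. The text supports neither. Nor should 44% be quoted alone: it belongs to 20 patients, while 40 is stated twice. Much higher adverse event miss rates can be had from an exact McNemar test, but the protocol does not specify that test.

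What does not stand is that this is only missing detail. Section 7 did not leave the method open. It chose a test, printed the formula and exempted no objective. Section 15.11 lists events without comparing masks and does not cover oxygenation or ventilation. A later analysis plan could add intervals, but section 7 would still state a method that does not fit the comparative objectives.

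**Conclusion.** The point holds in a limited form. The one comparative inference in the protocol cannot yield a favourable answer to the primary safety objective or to 3.2.1, whichever sample size applies. The gap is material at 20 patients and smaller at 40, where a 0.3-SD harm would still be missed in more than half of trials. These rates rest on assumed alpha, sidedness, effect size and type of SD, none of which the protocol gives. The zero-event bounds need only N and the confidence level. The finding is that the stated test could not support a conclusion of comparable safety, and it goes no further than that. The change should be made, since it is cheap and bears on the primary objective.

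**What to change.** In section 7, for the outcomes under 3.1 and 3.2.1, base conclusions on the within-patient Lumena-minus-standard estimate with its 95% confidence interval. For adverse events, add to 15.11 the paired risk difference with an exact interval or, if there are no events, the exact upper bound.

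State that a non-significant difference will not be read as evidence of safety, and that the conclusion will give the largest excess harm compatible with the upper confidence limit. Any claim that Lumena is as safe as the standard mask should require a clinically justified margin set before data are seen, with the upper limit below it. Without such a margin, the safety conclusion stays descriptive. Keep the difference test for aerosol reduction (3.2.2, 3.2.5), where superiority is the question.

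This takes a few sentences in a protocol amendment, repeated in any analysis plan, and adds no patients, visits or measurements. The downside is a less favourable safety statement, because the intervals are wide at these sample sizes.

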9.9. Claustrophobia

10. Possible device related Adverse Effects:

10.1. Device-Specific AE's:

10.1.1. Impaired patient ventilator synchrony

10.2. Non Device-Specific possible AE's include:

10.2.1. Barotrauma

10.2.2. Nausea

10.2.3. Feeling of claustrophobia

10.2.4. Facial and eye irritation

10.2.5. Facial pain due to pressure

11. Special Populations:

The study will not include special populations such as pregnant women, persons who are not able to provide informed consent or those under 18 years of age.

	Date 1 st Issued: 26.12.2021	
Title: Clinical trials protocol – “Lumena”; Safety and usability of the LUMENA non-invasive ventilation mask	Doc #: CL-003	Revision: 04
	Confidential	Page 11 of 20

12. Study device (Lumena mask) description:

[figure not shown]

Figure 1: Lumena Mask

The Disposable Single-Patient-Use “Lumena” Oro-Nasal mask is a transparent mask for administration of non invasive ventilation (NIV) designed to minimize aerosolization into the surrounding environment. Each mask may be used for up to 14 days.

The mask is an interface accessory for use with a positive pressure ventilation device such as a BiPAP/CPAP machines or a mechanical ventilator. All of the mask components are able to be cleaned.

The face piece consists of an internal volume for providing patient ventilation by a positive pressure, “covered” with an external layer kept at a sub-atmospheric pressure by a suction source (either a dedicated vacuum generator or a hospital wall suction) in order to continuously capture any air escaping from the internal volume. A circumferential sealing cushion is positioned between the internal volume and the external layer to minimize any escape of potentially contaminated air into the external layer. The Mounting Head Gear has straps that are adjustable and hold the Face Piece against the patient’s face while slightly squeezing the

	Date 1 st Issued: 26.12.2021	
Title: Clinical trials protocol – “Lumena”; Safety and usability of the LUMENA non-invasive ventilation mask	Doc #: CL-003	Revision: 04
	Confidential	Page 12 of 20

aforementioned sealing cushion, thus minimizing any potential gas leakage from the internal volume.

The “Lumena” is a non-vented mask that does not incorporate an integrated CO₂ exhaust vent in its design, and as such must be used only as part of a dual limb circuit or a single limb circuit that contains auxiliary CO₂ exhaust features. The mask is designed to be used in positive pressures ranging from 4-30 cmH₂O.

The mask is connected via a standard suction tube to a vacuum source that can provide at least 30 liter/minute of flow as a safe, aerosol minimizing device, but can also be used as a regular, non-safe NIV mask when it is not connected to a vacuum source. The mask contains two separate spaces, an inner space positively pressurized to administer positive pressure ventilation, and a separate, negatively pressurized space that scavenges aerosol emitted during ventilation and prevents it from being released into the surrounding environment.

The mask has been approved by the Israeli Ministry of Health’s Medical Devices Department ("AMAR"/ר"מ), approval #34860001.

[figure not shown]

Figure 2: Lumena gap Pathway

Title:

Doc #: CL-003

Revision: 04

[figure not shown]
Clinical trials protocol – “Lumena”;

Confidential

Page 13 of 20

Safety and usability of the LUMENA non-invasive ventilation mask

13. "Lumena"- Specific Components:

The mask, which is available in 3 sizes (Small, Medium, Large), consists of the following basic components:

1. Mask Frame, containing:
 - a. Suction port for connection to a vacuum source, either wall suction or a portable vacuum machine using via a 28Fr suction tube in order to maintain negative pressure in the mask's outer layer
2. Clip On
3. Quick-Release Clip
4. Elbow
5. Oxygen Port Cap
6. Suction & Inlet Tubes Gripper (*2 in kit)
7. Swivel lock Ring
8. Head Cushion
9. Inner Cushion
10. Outer Cushion
11. Headgear Strap
12. O-Ring
13. Suction Cap
14. Silicone Guard

	Date 1 st Issued: 26.12.2021	
Title: Clinical trials protocol – “Lumena”; Safety and usability of the LUMENA non-invasive ventilation mask	Doc #: CL-003	Revision: 04
	Confidential	Page 14 of 20

14. Study Description:

14.1. Enrollment phase:

All patients at the relevant departments who require non-invasive mechanical ventilation according to treating physician's decision will be screened for eligibility, given an investigator is available. Study eligibility will be determined by the inclusion and exclusion criteria. All eligible patients who meet study eligibility will be offered to participate in the study. Signed informed consent will be performed by research staff.

The offer to enroll shall be presented only by the investigators and will be presented to all eligible patients.

Consented patients will be randomized to one of four groups. Each group has a unique sequence protocol:

- A. 1) Standard NIV mask [30-60 minutes]; 2) Lumena mask without suction [30-60 minutes]; 3) Lumena mask with suction [30-60 minutes].
- B. 1) Standard NIV mask [30-60 minutes]; 2) Lumena mask with suction [30-60 minutes]; 3) Lumena mask without suction [30-60 minutes].
- C. 1) Lumena mask without suction [30-60 minutes]; 2) Lumena mask with suction [30-60 minutes]; 3) Standard NIV mask [30-60 minutes].
- D. 1) Lumena mask with suction [30-60 minutes]; 2) Lumena mask without suction [30-60 minutes]; 3) Standard NIV mask [30-60 minutes].

Data required for study purposes (see below) will be collected at time of enrollment from the medical record and/or from direct questioning of the study patient.

	Date 1 st Issued: 26.12.2021	
Title: Clinical trials protocol – “Lumena”; Safety and usability of the LUMENA non-invasive ventilation mask	Doc #: CL-003	Revision: 04
	Confidential	Page 15 of 20

14.2. Intervention phase:

Following randomization, each patient will be placed on BIPAP or a CPAP (per clinical need) using either the aerosol-reducing mask (Lumena) for approximately 1-2 hours, and then on the standard NIV mask used at the department for another 1-2 hours, or vice versa according to randomization scheme. In general, ventilation at each condition will be 30-60 minutes for each condition, with variation expected due to patient clinical need. Suction will be connected/disconnected from the Lumena mask according to the randomization schemes 30-60 minutes from placement of the mask. The patients will serve as their own control (cross over design).

During each of the three study phases (use of standard NIV mask, use of Lumina mask with suction and use of Lumina mask without suction), an inhalation of 5 ml 0.9% NaCl will be administered to the patient via the mask (using an in-line connector and a standard inhalation chamber) to enhance potential for environmental spread of small particles and thus enhance the ability to discriminate between the standard mask and the Lumina masks` ability to minimize aerosol spread.

Eligible patients will be enrolled into the study, perform trial activities and exit the study within a maximum of 1 day.

The study will be performed in a hospital intensive-care setting due to the nature of the device, and the required patients population.

	Date 1 st Issued: 26.12.2021	
Title: Clinical trials protocol – “Lumena”; Safety and usability of the LUMENA non-invasive ventilation mask	Doc #: CL-003	Revision: 04
	Confidential	Page 16 of 20

14.3. Monitoring:

During all phases of the study (either using standard NIV mask or Lumina mask), a staff member will be present in the patient's room.

Vital signs during NIV will be recorded in real time by the staff member.

Before, during and after NIV, and electrocardiogram (ECG) will be monitored and arterial blood\ venous gas (ABG\VBG) samples will be drawn.

A particle-measuring device (Particle Plus 8303) will be placed at a distance of 1.5 meter from the patient`s face to record the level of aerosol spread.

Following each session of NIV, the patient as well as the staff member treating the patient will be asked to complete a short questionnaire regarding the comfort and ease of use of each of the masks used. Any adverse events will be captured in real time by the staff member.

15. Data Collected:

15.1. Demographics including as age, sex, DOB, height, weight and body mass index.

15.2. Past medical history including smoking status, co-morbid conditions and medication use.

15.3. Vital signs before, during and after non-invasive ventilation such as: heart rate, respiratory rate, Tidal volume, oxygen saturation, Mode of ventilation, peak Inspiratory Pressure, Pressure Support, Ventilator type and model, Trigger sensitivity, Fio2%, PEEP, blood pressure (invasive and/or non-invasive), and temperature.

15.4. Electrocardiogram (ECG) diagrams before use (historical ECG can be also use) and monitoring during use.

Title:

Doc #: CL-003

Revision: 04

Clinical trials protocol – “Lumena”;
 Safety and usability of the LUMENA non-invasive ventilation mask

Confidential

Page 17 of 20

- 15.5. Arterial blood\ Venous blood gas analysis for O₂, CO₂, pH and HCO₃ as well as serum Lactate levels before, during and after non-invasive ventilation. A maximum of 20 ml of blood will be collected from each patient.
- 15.6. Symptoms and signs during use of non-invasive ventilation (e.g. diaphoresis, anxiety).
- 15.7. Estimation of patient preference of the mask- The question shall be phrased thusly: which mask do you prefer?
- 15.8. Estimation of staff comfort (an analog 1-5 scale as well as recording of verbal comments) – the question shall be phrased thusly: In a scale of 1-5, 1 being very uncomfortable and 5 being very comfortable, how would you rate the mask?
- 15.9. Estimation of staff use - The question shall be phrased thusly: which mask do you prefer?
- 15.10. Estimation of patient comfort – the question will be directed to the staff member. (an analog 1-5 scale as well as recording of verbal comments). – the question shall be phrased thusly: In a scale of 1-5, 1 being very uncomfortable and 5 being very comfortable ,how would you rate the patient's feeling with the experimental mask?
- 15.11. Device related adverse events will be reported by number, type, seriousness, severity , duration and attribution . All device and treatment related adverse events will be captured, regardless of severity.

16. Risk-Benefit Assessment

This is a feasibility proof of concept study, i.e. the nature and purpose of this study is to collect data to support research and development of the Lumena mask during noninvasive ventilation. The patients will have no direct health benefit from the use of the device.

	Date 1 st Issued: 26.12.2021	
Title: Clinical trials protocol – “Lumena”; Safety and usability of the LUMENA non-invasive ventilation mask	Doc #: CL-003	Revision: 04
	Confidential	Page 18 of 20

Expected benefit for patients and staff will arise from the future creation a safer care environment, potentially minimizing the need for bulky personal protective equipment (PPE).

The Lumena mask is considered class II device in Europe. Risk assessment has been performed and no major or intolerable risks were found. All the mitigations were documented. The risk management summary in the company’s IB demonstrates that the risks associated with the tested devices are well mitigated and are as low as reasonably practicable as defined by the applicable standards.

As for the Lumena mask usage, the protocol has been designed to decrease and minimize the risk to the patients by monitoring the respiratory parameters and using it for no more than an hour.

Expected adverse events like cough or bronchospasm may arise during inhalation study. Subjects will be monitored closely for safety and reporting of adverse events during the study including follow up until complete resolution of any adverse events.

17. Confidentiality and Information Security

Each patient will be assigned a unique identifying number and that number will be used throughout all data collection and analysis processes.

The mapping of study identifiers and patient details will be stored by the primary investigator in a locked cabinet or a password-protected hospital-issued computer. The mapping list will be deleted or physically destroyed after completion of data analysis, and a report of said deletion will be included in the study summary. This file will not be sent via unencrypted email nor will it be removed from hospital premises without written consent by the hospital’s R&D division.

	Date 1 st Issued: 26.12.2021	
Title: Clinical trials protocol – “Lumena”; Safety and usability of the LUMENA non-invasive ventilation mask	Doc #: CL-003	Revision: 04
	Confidential	Page 19 of 20

Only the primary and secondary investigators, who are hospital employees with permission to access medical records, will have access to the de-identified data. Specifically, the sponsor will not have access to de-identified patient data.

18. Study Duration:

18 months or until enrollment of 40 eligible patients (the first of both occurrences).

Each patient will be included for a maximum of one day, from enrollment and obtainment of informed consent until end of participation.

	Date 1 st Issued: 26.12.2021	
Title: Clinical trials protocol – “Lumena”; Safety and usability of the LUMENA non-invasive ventilation mask	Doc #: CL-003	Revision: 04
	Confidential	Page 20 of 20

19. References:

1. Hannah Ritchie, Edouard Mathieu, Lucas Rodés-Guirao, Cameron Appel, Charlie Giattino, Esteban Ortiz-Ospina, Joe Hasell, Bobbie Macdonald, Diana Beltekian and Max Roser (2020) - "Coronavirus Pandemic (COVID-19)". Published online at OurWorldInData.org. Retrieved from: 'https://ourworldindata.org/coronavirus' [Online Resource]
2. Sergio Alejandro Gómez-Ochoa, Oscar H Franco, Lyda Z Rojas, Peter Francis Raguindin, Zayne Milena Roa-Díaz, Beatrice Minder Wyssmann, Sandra Lucrecia Romero Guevara, Luis Eduardo Echeverría, Marija Glisic, Taulant Muka, COVID-19 in Health-Care Workers: A Living Systematic Review and Meta-Analysis of Prevalence, Risk Factors, Clinical Characteristics, and Outcomes, *American Journal of Epidemiology*, Volume 190, Issue 1, January 2021, Pages 161–175, <https://doi.org/10.1093/aje/kwaa191>

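### Mask durations in 14.1, 14.2 and section 16 conflict, so planned Lumena-to-standard exposure is 2:1 or 1:1 depending on which sentence is followed

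*Protocol*

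**What the plan says.** Section 14.1 lists four sequences. Each has one standard-mask period and two consecutive Lumena periods, all with the same bracketed time. Group A reads "Standard NIV mask [30-60 minutes]; 2) Lumena mask without suction [30-60 minutes]; 3) Lumena mask with suction [30-60 minutes" and group C reads "Lumena mask without suction [30-60 minutes]; 2) Lumena mask with suction [30-60 minutes]; 3) Standard NIV mask [30-60 minutes"; B and D differ only in the order of the two Lumena conditions.

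Section 14.2 opens with different totals. It plans about 1-2 hours of ventilation with Lumena. For the standard mask it says "and then on the standard NIV mask used at the department for another 1-2 hours"; the randomization scheme may reverse this order. Its next sentence returns to the per-condition time: "In general, ventilation at each condition will be 30-60 minutes for each condition, with variation expected due to patient clinical need". Suction is then switched on or off 30-60 minutes after the mask is placed, with no removal of Lumena scheduled between its two conditions. One saline inhalation is given in each of the three conditions.

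Section 16, in the risk-benefit argument, names a Lumena wear time of at most one hour as a risk-limiting measure.

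The primary objective (3.1) is safety of Lumena compared with standard masks. On reporting, 15.11 says "Device related adverse events will be reported by number, type, seriousness" and goes on to severity, duration and attribution. Section 15 does not list the time for which each condition was worn.

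**The concern.** Staff cannot follow 14.1 and the first sentence of 14.2 together for the standard mask, except when the period lasts exactly 60 minutes. Nor can they keep to the one-hour limit of section 16, read as a limit on the mask, and also give Lumena for longer than its scheduled minimum.

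The choice matters for the primary objective because it sets the exposure behind the comparison. Under one text Lumena has on average twice the wear time of the comparator; under the other the two are nominally equal. A count of adverse events by mask would then partly reflect time worn. Facial pressure pain (10.2.5) and comfort ratings may also depend on continuous wear, and in every sequence the two Lumena periods follow each other on one placement of the mask.

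**Working it through.** **Inputs.** Per-condition time 30-60 minutes (14.1; 14.2, second sentence). One standard and two Lumena conditions per patient (Table 1; 14.1). Totals of 1-2 hours on each mask (14.2, first sentence). Lumena at most one hour (section 16). One inhalation per condition (14.2). Number of patients: section 6 gives both 40 and four groups of five, so both 40 and 4 x 5 = 20 are shown.

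**Step 1: reproduce the totals in 14.2.** Time on a mask = number of conditions with that mask x 30-60 minutes.
- Lumena: 2 x 30 = 60 to 2 x 60 = 120 minutes. This reproduces the 1-2 hours.
- Standard: 1 x 30 = 30 to 1 x 60 = 60 minutes. This does not reproduce 1-2 hours (60-120 minutes); the ranges meet only at 60 minutes.

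**Step 2: compare with section 16.** Lumena at 60-120 minutes meets a limit of 60 minutes only if both Lumena conditions last their minimum of 30 minutes. If the hour is meant per condition, it fits, but section 16 does not say so.

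**Step 3: exposure ratio, Lumena to standard.**
- 14.1, equal period lengths: 2:1. Lowest: (30 + 30)/60 = 1. Highest: (60 + 60)/30 = 4.
- 14.2, first sentence, midpoints: 90/90 = 1. Lowest: 60/120 = 0.5. Highest: 120/60 = 2.
- Spread under 14.1, assuming that each period varies independently and uniformly over 30-60 minutes: median ratio 2.0, with 95% of patients between 1.29 and 3.21, and 89% above 1.5.

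**Step 4: expected counts if events were pooled by mask.** Expected count = patients x hours x hazard. Assumptions: the same constant hazard of 0.1 events per hour on both masks, and durations at their midpoints.

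| Schedule | Patients | Lumena | Standard |
|---|---|---|---|
| 14.1 | 20 | 20 x 1.5 x 0.1 = 3.0 | 20 x 0.75 x 0.1 = 1.5 |
| 14.1 | 40 | 40 x 1.5 x 0.1 = 6.0 | 40 x 0.75 x 0.1 = 3.0 |
| 14.2, first sentence | 20 | 20 x 1.5 x 0.1 = 3.0 | 20 x 1.5 x 0.1 = 3.0 |
| 14.2, first sentence | 40 | 40 x 1.5 x 0.1 = 6.0 | 40 x 1.5 x 0.1 = 6.0 |

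The ratio does not depend on the hazard chosen; the counts do. Counting patients with any event, 1 - exp(-hazard x hours), hardly changes this under 14.1. At 0.05 per hour the ratio is 0.0723/0.0368 = 1.96; at 0.5 per hour it is 0.528/0.313 = 1.69.

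**Step 5: the same counts by condition.** With 20 patients under 14.1, each of the three conditions has 20 x 0.75 x 0.1 = 1.5 expected events. The imbalance disappears.

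**Step 6: inhalations.** Two on Lumena and one on the standard mask, so 2:1 by mask whichever duration is followed, and 1:1:1 by condition. Section 16 expects cough or bronchospasm from the inhalation, so this imbalance could affect pooled counts as well.

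**The case against.** The best defence is that the protocol is organised by three conditions throughout: Table 1, the sequences in 14.1 and the inhalations in 14.2. Under 14.3 a staff member is present in all phases and captures events in real time, so each event can be assigned to a condition. Section 15.11 lists attributes of events; it does not say that the two Lumena conditions are added together. Event rates may be specified in the statistical analysis plan, which is not shown. This stands. A reader might infer that the primary safety comparison is already invalid, or that the masks cannot be compared; the text does not support that. The distortion arises only if counts are pooled by mask.

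Three other stronger readings also fail.
- That every patient wears Lumena twice as long: 2:1 is the scheduled average, and 14.1 allows 1:1 to 4:1 in one patient.
- That sites would follow different sentences: the protocol describes one hospital setting and mentions no second site. Different readings by staff remain possible.
- That staff may choose durations freely: 14.2 ties the variation to the patient's clinical need.

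The doubled count also needs a constant hourly hazard. Events triggered by fitting the mask, such as a feeling of claustrophobia (10.2.3), need not grow with time, and Lumena is placed only once.

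Finally, it can be said that a single loosely worded sentence is out of line, in a study that section 16 calls a feasibility proof of concept. That lowers the weight of the reporting point. It does not remove the conflict: allowing for variation does not make one 30-60 minute condition a planned 1-2 hours, and section 16 adds a third figure. An analysis plan cannot settle contradictory instructions to bedside staff.

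**Conclusion.** The schedule conflict is a firm error in the current text. The standard mask is given 30-60 minutes in 14.1 and the second sentence of 14.2, but 1-2 hours in the first sentence of 14.2. Lumena is scheduled for 60-120 minutes in 14.1 and 14.2, but limited to one hour in section 16. Planned Lumena-to-standard exposure is accordingly 2:1 on average or nominally 1:1.

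The consequence for the safety comparison is conditional. If events were pooled by mask, and if hazards were equal and constant over time, the expected count ratio would be about 2:1 under 14.1 with no true difference between masks. The 0.1 events per hour is an illustration, not a figure from the protocol. Counts by the three conditions have similar planned exposure and one inhalation each. The reporting part is therefore a recommendation of lower weight than the correction of the schedule.

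**What to change.** 1. Reconcile the durations in 14.1, both sentences of 14.2 and section 16, and say whether the hour in section 16 applies to each condition or to the mask as a whole. Which duration is right is for the sponsor to decide.
2. Add the actual start and stop time of each of the three conditions to section 15. Durations are expected to vary, and hourly rates need the true wear time.
3. State in 15.11 that adverse events are reported for the standard mask, Lumena with suction and Lumena without suction separately, as patients with an event and as events per hour worn, and not as raw counts pooled by mask.

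The cost is a wording amendment, two clock times per condition (six per patient) on the case report form, and one more column in the safety table. No procedure is added.
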